C.3.5 Intervention. The study intervention will include a single arm given (1) 6H: 300 mg INH daily for 6 months. All participants will also receive 25 mg pyridoxine (vitamin B-6) daily for the treatment duration to reduce the risk of INH-induced peripheral neuropathy.¹¹¹ Patients will be encouraged to continue taking all other concurrently prescribed drugs (i.e., ART and cotrimoxazole). Patients will receive adherence advice, advice to avoid hepatotoxic substances (e.g. acetaminophen, alcohol, herbal medicines), instructions on monitoring side effects, phone numbers for contacting the medical staff in case of serious side effects, and instructions on using the EMM bottle like a regular medicine bottle. The pills will be dispensed at the pharmacy where the participants receive their ART.

C.3.6 Follow-up study visits. Assessments for toxicity will occur week 2 and months 1 through 7 (Table 3). A clinical officer will screen for symptoms of hepatotoxicity and other side effects using a Case Report Form (CRF) based on the TEMPRANO ANRS adverse event grading⁶ and perform ALT/AST testing. Treatment will be stopped if a patient develops a Grade 3/4 toxicity, as determined by the study physician. In addition, the monthly study visits while on medication will include pharmacy pill counts, EMM data downloads, and brief surveys on alcohol use and adherence. Hair collection will occur at 3 and 6 months. Blood collection will occur at baseline (for PEth, CD4 cell count, HIV viral load, and repository storage), 3 and 6 months, and every 6 months thereafter. Participants will also be given a card with phone numbers to contact the clinical staff if side effects occur between study visits; if side effects occur, participants will be asked to come in for additional ALT/AST testing and follow-up. These calls and visits will also be recorded in a CRF. All CRFs will be reviewed weekly by the study physician. Screening for symptoms for active TB, and sputum testing and chest X-ray if symptoms are reported, will occur at every follow-up visit, including those after the completion of the trial. High retention will be maintained as in our prior studies using follow up phone calls, alerts when patients come to the ISS clinic, and home visits when needed.

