Adherence and treatment default. In each month while taking TB preventive therapy, simulated individuals have a probability of non-adherence and/or treatment default, i.e. treatment discontinuation that is unrelated to hepatotoxicity. Simulated patients who stop medications do not accrue the full benefit of prevention, though incomplete courses of therapy confer partial preventive benefits.²¹ One challenge to incorporating treatment adherence data in a decision analytic model is that the effectiveness of various levels of adherence to TB preventive therapy is not known. We will therefore model discontinuation/default and low adherence in two ways: First, we will use WHO definitions of treatment loss to follow-up for active tuberculosis treatment to model TB preventive therapy adherence as a binary outcome (yes/no).⁹ We will define "not adherent" as any patient who misses two consecutive monthly refill visits, or who, for 2 consecutive months, self-reports taking <80% of his/her intended doses of therapy, or whose EMM cap data indicates <80% of doses taken. In the simulation model, individuals will not accrue any benefits (or risks) of therapy after the month that the patient is classified as "non-adherent." Second, we will use EMM adherence data to model non-adherence as a continuous outcome. We will assume that taking fewer than the total number of TB preventive therapy doses throughout the entire course of therapy has the same effect as taking 100% of doses for fewer months than recommended. For example, we will assume that taking 50% of doses for six months of therapy provides similar treatment efficacy as taking 100% of all doses for only 3 months. We will compare the results of these two strategies and thus gain information on the relative importance of how adherence is modeled.

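### The Aim 3 binary adherence rule counts one or two drug-free months as therapy for people who stop INH, and credits a stop after month 5 as a full course

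*Combined protocol and SAP*

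**What the plan says.** The course is "300 mg INH daily for 6 months" (C.3.5). The adherence paragraph of C.4.2 covers poor adherence and discontinuation unrelated to hepatotoxicity; stops for toxicity are modelled separately. It describes two strategies.

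The first is binary. A participant is not adherent if any one of three criteria is met:

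- refills: "any patient who misses two consecutive monthly refill visits";
- self-report: "for 2 consecutive months, self-reports taking <80% of his/her intended doses of therapy";
- EMM: "or whose EMM cap data indicates <80% of doses taken", with no time window of its own.

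The consequence in the model is that "individuals will not accrue any benefits (or risks) of therapy after the month that the patient is classified as" non-adherent. No sentence dates the end of therapy to the last dose.

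The second strategy is continuous and credits the share of doses taken according to EMM. Of the two, the plan says: "We will compare the results of these two strategies and thus gain information on the relative importance of how adherence is modeled".

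The same paragraph states the principle that both should respect: "Simulated patients who stop medications do not accrue the full benefit of prevention". It adds that an incomplete course still gives part of the benefit.

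**The concern.** Classification is an event of recognition, and it comes after the drug has stopped. Because credit runs to the end of the month of classification, the months that trigger the rule are themselves modelled as months on therapy. They carry both TB protection and INH toxicity risk, though no drug was taken. Someone who stops late enough is credited with the whole course, contrary to the principle quoted above.

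Two things are at stake. Treatment credit feeds the Aim 3 contrasts in C.4.4, including therapy without monitoring against no therapy, and the model gives therapy a five-year effect. And the planned comparison of the two strategies is meant to show how much the modelling of adherence matters. Part of any difference would instead be a lag in the date of classification.

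**Working it through.** **The plan's own figure.** The only worked credit in this paragraph is for the continuous strategy: half the doses for six months equals three full months. Share of doses × 6 = 0.5 × 6 = 3.0, which reproduces. The plan gives no worked figure for the binary rule.

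**Inputs.** Course of 6 months (C.3.5); the three criteria and the end-of-credit sentence (C.4.2). Assumptions: the participant takes every dose through month k and none afterwards, and k = 1 to 5 are equally likely.

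**Formula.** Let m be the first month in which a criterion is met. Months credited = m, or 6 if none is met by month 6. Excess = months credited − k. Since the EMM window is not stated, three readings are needed:

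- Single month: month k+1 has 0% of doses, so m = k+1.
- Cumulative: the share at the end of month k+1 is k/(k+1), that is 50%, 67% and 75% for k = 1, 2, 3, so m = k+1. For k = 4 it is 4/5 = 80%, which is not below 80%; the criterion is met in month 6 (4/6 = 67%). For k = 5 it is 5/6 = 83%, so it is never met.
- Two consecutive months: m = k+2 for k = 1 to 4. For k = 5 only one failing month remains, so it is never met.

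| Stop after month (= months taken) | Single month | Cumulative | Two consecutive months |
|---|---|---|---|
| 1 | 2 | 2 | 3 |
| 2 | 3 | 3 | 4 |
| 3 | 4 | 4 | 5 |
| 4 | 5 | 6 | 6 |
| 5 | 6 | 6 | 6 |
| Mean (taken: 3.0) | 4.0 | 4.2 | 4.8 |
| Mean excess | 1.0 | 1.2 | 1.8 |
| Credited a full course | 1/5 = 20% | 2/5 = 40% | 2/5 = 40% |

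The cumulative result for k = 4 sits exactly on the threshold. One earlier missed dose would classify that person in month 5, with 5 months credited.

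**Refill criterion.** If month k is the last month dispensed, the visits at months k and k+1 are missed and m = k+1. Credits are then 2/3/4/5/6, an excess of 1.0, whatever the EMM window. If the participant attends visit k and only then drops out, the misses are at k+1 and k+2, and this criterion acts no sooner than the two-month reading.

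**Illustration of what a credited month is worth.** Table 4 gives hazard ratios for active TB of 0.11–0.41 for full adherence and 0.25–0.91 for half. Interpolating on the log scale (an assumption), a fraction f of the course has HR = HR50 × (HR100/HR50)^((f − 0.5)/0.5). With the Table 4 incidence of 3.41 per 100 person-years held for 5 years, cases per 1000 = 1000 × (1 − exp(−0.0341 × 5 × HR)).

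- Stop after month 5 (f = 5/6): HR 0.145–0.535, about 24–87 cases, against 19–68 when credited as a full course.
- Stop after month 4 (f = 4/6): HR 0.19–0.70, about 32–112 cases, against the same 19–68 on the readings that credit a full course.

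**The opposite error.** A participant steadily taking 50% of doses is classified in month 1 (single month or cumulative) or month 2 (two months). The continuous strategy gives 3.0 months. At a steady 70% the figures are 1 or 2 months against 0.7 × 6 = 4.2.

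**The case against.** The strongest reply is that much of the size depends on how the rule is read. A reader might infer that two consecutive months below 80% are needed under every adherence measure, so that people who stop gain 1.8 months on average, 40% get a full course, and a stop after month 4 always counts as six months. The text does not support that as fact. The two-month phrase is attached to self-report; the EMM criterion has no window; and the criteria are joined by an alternative, so the earliest one classifies. This stands, and the result has to be given as a range.

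A reader might also scale the excess to the whole cohort with the completion rates in the Background (82–87%, or 34%). That is not sound. Those non-completers can include people who stopped for toxicity, whom this rule does not cover, and the 34% comes from a 9-month course.

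Third, a reader might infer that the rule favours treatment. That is not established: toxicity risk runs through the same extra months, and steady partial takers lose credit.

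Fourth, the plan already has a continuous strategy based on doses taken, and C.4.5 lists imperfect adherence as a candidate for probabilistic sensitivity analysis. Both limit the damage, and the comparison of strategies is not made worthless. But neither corrects the binary rule, and the comparison cannot separate the lag from the choice of strategy.

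Finally, the end-of-credit sentence could mean that all protection is lost at classification. That would sit badly with the paragraph's own statement on partial benefit, and a late stop that is never classified would still count as a full course.

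**Conclusion.** The concern holds in a limited form. For an abrupt stop at a month's end, unrelated to hepatotoxicity, the binary rule credits at least one drug-free month and at most two. With stops spread evenly after months 1 to 5, the mean excess is 1.0 month (single-month EMM), 1.2 (cumulative) or 1.8 (two consecutive months); the last two fall towards 1.0 where missed refills act first. A stop after month 5 is a full course on every reading. A stop after month 4 is one only on the cumulative and two-month readings, and only if the refill criterion has not acted sooner.

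This conflicts with the section's own principle for people who stop, and it puts both modelled benefit and modelled risk into months without drug. The documents do not allow a statement about the net effect on life expectancy, or about the direction of bias. The TB counts above rest on an assumed interpolation and show scale only. The continuous strategy is unaffected.

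**What to change.** Keep the binary rule for identifying non-adherence, and change three things in C.4.2:

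1. For participants who stop INH, defined as no further EMM openings, end modelled benefit and risk at the month of the last opening. Apply this also to those who stop too late to be classified. The credits in the table then become 1/2/3/4/5 and the excess is zero.
2. Do not backdate for participants who keep taking doses below 80%. Ending their credit at the last month with at least 80% would give a steady 70% taker zero months, against 4.2 under the continuous strategy, and so widen the opposite error.
3. State whether the EMM criterion applies to a single month, to two consecutive months or cumulatively.

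The cost is a short addition to the model specification and the recoding of one input. EMM data are downloaded at the monthly visits and uploaded weekly (C.3.6, C.3.7), so nothing new is collected. The downside is slightly less credited benefit for people who stop. The Background notes that EMM misreads people who take out several pills at once; the pharmacy pill counts already planned can serve as a check on the last opening.

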TB epidemiology. The simulation model generates a cohort using the distribution in the target population of age, sex, prevalence of positive TSTs (>5 mm induration), and prevalence of sub-clinical (asymptomatic, so not identified) active TB. We will stratify all demographic and epidemiologic parameters by level of self-reported alcohol use at baseline, as above (any current drinking, heavy drinking, and very heavy drinking – see C.3.9), using the AUDIT-C that is available to treating clinicians in the real-world.

TB preventive therapy. The simulation of TB preventive therapy includes treatment discontinuation due to hepatotoxicity, as well as poor adherence or default. The model is structured to simulate any TB preventive treatment regimen. All parameters related to TB preventive therapy are regimen-specific and we will stratify them by level of alcohol use. We will model the benefits of TB preventive therapy as a relative reduction in the

Table 4: Select model parameters for decision model proposed in Aim 3.

	Parameter estimates	Data source
TB epidemiology		
Age/sex demographics		ADEPTT
Prevalence reactive TST		ADEPTT
Prevalence subclinical TB at baseline	0.085-0.094	135,136
Level of alcohol use prior to therapy		ADEPTT
TB preventive therapy		
Transitions between AST/ALT categories		ADEPTT
Probability of symptoms by AST/ALT	0.35	137
Toxicity-related mortality by AST/ALT	0.0-0.05	137-139
Adherence		ADEPTT
Health state utility for those with hepatotoxicity	0.65-1.0	140
Health state utility for those w/o hepatotoxicity	0.82-1.0	140
Progression to TB and TB mortality		
Incidence TB (per 100 person-years)		141-143
TST positive	3.41	
TST negative	3.06	
Hazard ratio for active TB		144-147
100% adherence vs. no therapy	0.11-0.41	
Partial (50%) therapy vs. no therapy	0.25-0.91	
TB-related case-fatality proportion	0.23	148
Health state utility with active TB	0.66-0.85	140
HIV and other non-TB mortality		
Life expectancy (starting age 31) CD4 >500	66 years	149-152
Standardized mortality ratio by CD4 count		151-154
CD4 350-499 cells/mm ³	3.5	
CD4 200-349 cells/mm ³	5.6	
CD4 <200 cells/mm ³	30.3	
Health state utility for HIV-infected persons	0.62-1.0	155-157

rate of progression to active TB. In the model, patients with sub-clinical TB do not benefit from the preventive therapy.

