Progression to active TB and death. Individuals in the simulation model will have a monthly probability of developing active TB that is stratified by drinking status.^{141,158} Those who develop active TB experience increased mortality and decreased quality of life. In addition, a portion of simulated patients with active TB will develop drug resistant disease, characterized by longer treatment courses, higher mortality, and lower quality of life than drug sensitive disease. We will model the effectiveness of TB preventive therapy as a relative reduction in the rate of developing active TB. A complete course of 6H provides a 30-50% reduction in reactivation,⁴⁻⁸ with a larger absolute reduction in TB incidence among those who have reactive TST than in those who do not. Studies among HIV-infected persons in settings of TB incidence, similar to Uganda, demonstrate that the benefits of TB preventive therapy are durable for five years.^{145,159} We will therefore model a 5-year reduction in the incidence of active TB, followed by a rapid return to the baseline TB incidence.

Competing risks of death Individuals in the existing model have an age- and sex-stratified risk of death from causes other than TB. In this proposed analysis of TB preventive therapy in HIV-infected persons in Uganda, the competing risks of death will reflect mortality related to HIV infection and all other non-TB mortality.

C.4.3 Data sources for the model. Whenever possible, we will use the novel data from Aims 1 and 2 of this study (Table 4, denoted as ADEPTT) for model parameters. Other model parameters will be obtained from the medical literature.

TB epidemiology. The ADEPTT cohort will inform the age and sex distributions, and the prevalence of reactive TST (>5 mm) at baseline and level of self-reported alcohol use. We will use published reports of the prevalence of subclinical TB from established African cohorts.^{135,136}

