TB preventive therapy. The ADEPTT study includes frequent assessment of ALT/AST and symptoms. These data, stratified by level of self-reported alcohol consumption, will inform all of the parameters governing movement between toxicity-related health states. Because the study will stop treatment at the identification of any Grade 3/4 hepatotoxicity, we anticipate no medication-related deaths in ADEPTT. Therefore, we will use the medical literature to inform mortality from each toxicity-related health state in the model, as well as the health state utility of patients with toxicity-related symptoms.¹³⁷⁻¹⁴⁰

Progression to active TB and death. Because the number of observable cases of active TB in the cohort after therapy is expected to be low, we will use the medical literature to inform the incidence of active TB, stratified by TST status, without preventive therapy,¹⁴¹⁻¹⁴³ and will account for the reported efficacy of TB preventive therapy.¹⁴⁴⁻¹⁴⁷ We will use reports of health state utility with active TB collected in SSA.¹⁴⁰

Competing risks of death. We will estimate mortality from all causes other than TB using long-term follow-up of cohorts of HIV-infected persons in SSA. We will use the literature to estimate non-TB mortality among a cohort of HIV-infected persons on ART in SSA with baseline CD4>500¹⁴⁹⁻¹⁵² and published reports of the HR for mortality by lower CD4 counts.¹⁵¹⁻¹⁵⁴ We will also use the medical literature to estimate health state utilities for HIV-infected individuals with and without TB.

C.4.4 Aim 3 analyses. We will use the model to simulate the long-term outcomes of a cohort of HIV-infected drinkers in Uganda with demographic and clinical characteristic similar to those of the ADEPT-TB cohort assuming that TB preventive therapy is provided to all HIV-infected patients who drink alcohol using each of the following TB preventive therapy and monitoring strategies:

- (1) No therapy (standard of care)
- (2) TB preventive therapy without hepatotoxicity monitoring unless patient is symptomatic (no monitoring)
- (3) TB preventive therapy with hepatotoxicity monitoring at week 2 of therapy only (week 2 monitoring)
- (4) TB preventive therapy with hepatotoxicity monitoring monthly throughout (monthly monitoring)

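### Section C.4.2 gives two non-overlapping effects for a full 6H course (30-50% reduction in the text, HR 0.11-0.41 in Table 4) and does not say how they relate

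*Combined protocol and SAP*

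**What the plan says.** The text of C.4.2, under progression to active TB and death, sets the scale first: "We will model the effectiveness of TB preventive therapy as a relative reduction in the rate of developing active TB". The next sentence gives the size, citing references 4-8: "A complete course of 6H provides a 30-50% reduction in reactivation". The Specific Aims and the Background give the same 30-50%, there for active TB and mortality together.

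Table 4, also in C.4.2, is headed "Select model parameters for decision model proposed in Aim 3". Its hazard ratios for active TB cite references 144-147:

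- "100% adherence vs. no therapy": 0.11-0.41
- "Partial (50%) therapy vs. no therapy": 0.25-0.91

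C.4.3, on data sources, says the model "will account for the reported efficacy of TB preventive therapy" and cites references 144-147 again. It gives no value and does not mention the 30-50%.

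Two other parts of C.4.2 bear on how the figures might be reconciled. Table 4 lists "Prevalence subclinical TB at baseline" as 0.085-0.094, and the text says that "patients with sub-clinical TB do not benefit from the preventive therapy". The adherence subsection reduces the benefit for people who miss doses or stop early.

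C.4.5 plans one- and two-way deterministic sensitivity analyses and a probabilistic one. It names efficacy as a candidate for the latter, but states no best estimate, range or distribution for it.

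**The concern.** Both statements describe the effect of a full course, in one section, for one model. On the scale the plan sets, the weakest effect in Table 4 (59%) is stronger than the strongest effect in the text (50%).

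Full-course efficacy is a main input on the benefit side of the first comparison in C.4.4, therapy without monitoring against no therapy. Two things are at stake.

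- **Size and traceability of the benefit.** A reader cannot tell which figure drives the projected TB cases averted, or how far the result depends on that choice.
- **Possible double discounting.** If the 30-50% is an as-given effect that already contains non-adherence, feeding it into the adherence modelling would discount it twice. That modelling should act only on a full-adherence HR.

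Also, if the full-course sensitivity range is taken from the ends of Table 4, the plan's own less favourable figure is never tested for a full course. The partial-therapy row reaches those values, but only for partial adherence.

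**Working it through.** Both ranges are literature inputs. The plan derives neither from the other, so there is no stated calculation to reproduce. The check is whether any reading makes them agree, and what the difference is worth.

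**1. One scale.** HR = 1 − relative reduction.

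- Text: 1 − 0.50 = 0.50 and 1 − 0.30 = 0.70.
- Table 4: 1 − 0.41 = 59% and 1 − 0.11 = 89%.
- Gap between the nearest ends: 0.50 − 0.41 = 0.09.

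**2. Is the 30-50% a 5-year risk reduction rather than a rate reduction?** Inputs: 3.41 cases per 100 person-years (Table 4, TST positive) and 5 years of effect (C.4.2). Risk(HR) = 1 − exp(−0.0341 × 5 × HR), so the untreated risk is 15.68%.

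- 50% reduction: −ln(1 − 0.1568 × 0.5)/0.1705 = 0.48.
- 30% reduction: −ln(1 − 0.1568 × 0.7)/0.1705 = 0.68.

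Both stay above 0.41, so a change of scale does not close the gap.

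**3. Does it count subclinical TB as unpreventable?** All TB = s + (1 − s) × Risk(HR), with s from Table 4.

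| s | Untreated | HR 0.11 (reduction) | HR 0.41 (reduction) |
|---|---|---|---|
| 0.085 | 22.84% | 10.20% (55.3%) | 14.68% (35.7%) |
| 0.094 | 23.60% | 11.08% (53.0%) | 15.52% (34.3%) |

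On this reading Table 4 becomes a 34-55% reduction in all TB, close to 30-50%. But the text says reactivation, which does not describe TB already present at baseline.

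**4. Is it an as-given effect, diluted by non-completion?** The Background cites completion of 82-87%, and 34% for a 9-month course in Uganda. Assume that non-completers get no benefit, and multiply completion by the Table 4 reduction.

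- 82-87% completion: 0.82 × 59% = 48% up to 0.87 × 89% = 77%.
- 34% completion: 0.34 × 59% = 20% up to 0.34 × 89% = 30%.

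These touch 30-50% without fully reproducing it. The text's own words, a complete course, count against this reading.

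**5. Size if both are the same full-course HR.** Constant hazard, no competing death, no drinking multiplier; case fatality 0.23 (Table 4). Per 100 people over 5 years:

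| HR | Risk, % | Cases averted | TB deaths averted |
|---|---|---|---|
| 1 | 15.68 | – | – |
| 0.11 | 1.86 | 13.82 | 3.18 |
| 0.41 | 6.75 | 8.92 | 2.05 |
| 0.50 | 8.17 | 7.50 | 1.73 |
| 0.70 | 11.25 | 4.43 | 1.02 |

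Ratios of cases averted:

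- Matched ends: 13.82/7.50 = 1.84 and 8.92/4.43 = 2.02.
- Nearest ends: 8.92/7.50 = 1.2.
- Farthest ends: 13.82/4.43 = 3.1.

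If the Background's three-fold TB risk in heavy drinkers is applied to 3.41 (an assumption), cases averted are 21.1-34.6 against 9.9-17.5, with matched-end ratios of 2.0-2.1.

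**6. Crude check on direction.** Take toxicity of 2.6-5.5% (C.3.9) and toxicity mortality of at most 0.05 (Table 4, read as per event, an assumption).

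- 0.026 × 0.05 = 0.13 deaths per 100.
- 0.055 × 0.05 = 0.28 deaths per 100.

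Against these stand 1.02 TB deaths averted per 100 at HR 0.70. The check ignores repeated monthly risk, utilities and any extra toxicity in drinkers.

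**The case against.** The strongest reply is that the input can be identified. Table 4 is headed as the Aim 3 parameters, C.4.3 assigns efficacy to the same references 144-147, and references 4-8 do not appear there. The Table 4 row already states its estimand, full adherence, and has a separate 50% row. On this view the 30-50% is a background figure repeated loosely. Much of this stands: a modeller following C.4.3 would use Table 4. It does not explain the sentence in C.4.2, which ties 30-50% to a complete course directly after defining the modelled scale.

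It is also fair that the missing point value is not peculiar to efficacy. Table 4 gives ranges alone for subclinical TB, toxicity mortality and the utilities. And C.4.5 already plans sensitivity analyses, without making the ends of Table 4 hard limits. So it is not established that HR 0.50-0.70 would go untested, only that nothing ensures it is tested.

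A reader might infer three stronger things that the documents do not support.

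- **That the projected benefit is overstated two-fold.** The ratio holds only if both figures are the same quantity. On the subclinical reading the gap nearly closes.
- **That the Aim 3 conclusion could reverse.** Nothing shows this. Both ranges favour therapy, and the crude check keeps its direction at HR 0.70.
- **That the shared source proves an error.** References 8 and 146 are the same South African cohort study, but the documents do not show which estimate each citation uses, and one study can supply several.

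**Conclusion.** The inconsistency is real. Read as written, C.4.2 gives a full 6H course HR 0.50-0.70 in its text and HR 0.11-0.41 in Table 4, and nothing in the plan connects them. Table 4 is very likely the input. The unresolved part is what the 30-50% measures: two explanations are plausible, neither is stated, and the wording of the sentence counts against each.

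The size is conditional. If the two figures are one full-course HR, with the incidence, horizon and simplifications given in the working, the projected cases averted differ about two-fold at matched ends and by 1.2 to 3.1 across the ranges. If they are different quantities, these ratios are not like for like. The issue is the magnitude and traceability of the Aim 3 benefit, not its demonstrated direction. Aims 1 and 2 do not use this input.

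**What to change.** Reconcile the C.4.2 text, Table 4 and C.4.3.

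1. Confirm Table 4 as the base-case source for full-course efficacy, and give a point value with the range.
2. Label the 30-50% in C.4.2 as what it is (for example as-given, or all TB including subclinical), or correct it. State that the adherence modelling in C.4.2 is applied only to a full-adherence HR.
3. Extend the deterministic sensitivity analysis of full-course efficacy already planned in C.4.5, for no monitoring against no therapy, to HR 0.70.

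The cost is a wording edit and one extra model run, with no effect on participants, sample size or data collection. The downside for the sponsor is that the projected benefit may look less favourable at the far end of the range.
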